962 event is not necessarily serious. For example, itching for several days may be rated as severe, but
963 may not be clinically serious.

964 • MILD: Usually transient, requires no special treatment, and does not interfere with the
965 participant's daily activities.

966 • MODERATE: Usually causes a low level of inconvenience or concern to the participant
967 and may interfere with daily activities but is usually ameliorated by simple therapeutic
968 measures.

969 • SEVERE: Interrupts a participant's usual daily activities and generally requires systemic
970 drug therapy or other treatment.

CLINICAL PROTOCOL

971 **11.6 Coding of Adverse Events**

972 Adverse events will be coded by the Study PI per the UVA IRB website instructions (i.e. mild,
973 moderate, severe). The study PI will review the investigator assessment of causality and may
974 agree or disagree. The study PI assessments will be recorded. The study PI will have the final say
975 in determining the causality.

976 Adverse events that continue after the participant's discontinuation or completion of the study
977 will be followed until their medical outcome is determined or until no further change in the
978 condition is expected.

979 **11.7 Outcome of Adverse Events**

980 The outcome of each reportable adverse event will be classified by the investigator as follows:

- 981 • RECOVERED/RESOLVED – The participant recovered from the AE/SAE without sequelae.
982 Record the AE/SAE stop date.
- 983 • RECOVERED/RESOLVED WITH SEQUELAE – The event persisted and had stabilized
984 without change in the event anticipated. Record the AE/SAE stop date.
- 985 • FATAL – A fatal outcome is defined as the SAE that resulted in death. Only the event that
986 was the cause of death should be reported as fatal. AEs/SAEs that were ongoing at the
987 time of death; however, were not the cause of death, will be recorded as “resolved” at
988 the time of death.
- 989 • NOT RECOVERED/NOT RESOLVED (ONGOING) – An ongoing AE/SAE is defined as the
990 event was ongoing with an undetermined outcome.
- 991 • An ongoing outcome will require follow-up by the site in order to determine the final
992 outcome of the AE/SAE.
- 993 • The outcome of an ongoing event at the time of death that was not the cause of death,
994 will be updated and recorded as “resolved” with the date of death recorded as the stop
995 date.
- 996 • UNKNOWN – An unknown outcome is defined as an inability to access the participant or
997 the participant's records to determine the outcome (for example, a participant that was
998 lost to follow-up).

999 All clinically significant abnormalities of clinical laboratory measurements or adverse events
1000 occurring during the study and continuing at study termination should be followed by the
1001 participant's physician and evaluated with additional tests (if necessary) until diagnosis of the
1002 underlying cause, or resolution. Follow-up information should be recorded on source documents.

1003 If any reported adverse events are present when a participant completes the study, or if a
1004 participant is withdrawn from the study due to an adverse event, the participant will be

CLINICAL PROTOCOL

1005 contacted for re-evaluation within 2 weeks. If the adverse event has not resolved, additional
1006 follow-up will be performed as appropriate. Every effort should be made by the Investigator or
1007 delegate to contact the participant until the adverse event has resolved or stabilized.

1008 **11.8 Reportable Device Issues**

1009 All UADEs, ADEs, device complaints, and device malfunctions will be reported irrespective of
1010 whether an adverse event occurred, except in the following circumstances.

1011 The following device issues are anticipated and will not be reported but will reported as an
1012 Adverse Event if the criteria for AE reporting described above are met:

- 1013 • Component disconnections
- 1014 • CGM sensors lasting fewer than the number of days expected per CGM labelling
- 1015 • CGM tape adherence issues
- 1016 • Pump infusion set occlusion not leading to ketosis
- 1017 • Battery lifespan deficiency due to inadequate charging or extensive wireless
1018 communication
- 1019 • Intermittent device component disconnections/communication failures not leading to
1020 system replacement
- 1021 • Device issues clearly addressed in the user guide manual that do not require additional
1022 troubleshooting
- 1023 • Skin reactions from CGM sensor placement or pump infusion set placement that do not
1024 meet criteria for AE reporting

1025 **11.9 Timing of Event Reporting**

- 1026 • UADEs must be reported within 10 working days to the FDA after the sponsor first
1027 receives notice of the adverse effect.
- 1028 • Other reportable adverse events, device malfunctions (with or without an adverse event)
1029 and device complaints should be reported promptly, but there is no formal required
1030 reporting period.
- 1031 • The IDE Sponsor will investigate the UADE and if indicated, report the results of the
1032 investigation to the IRBs FDA and DSMB within 10 working days of the study team
1033 becoming aware of the UADE per 21CFR 812.46(b) (2).
- 1034 • The FDA and DSMB will determine if the UADE presents an unreasonable risk to
1035 participants. If so, the Study PI must ensure that all investigations, or parts of
1036 investigations presenting that risk, are terminated as soon as possible but no later than 5

CLINICAL PROTOCOL

1037 working days makes this determination and no later than 15 working days after first
1038 receipt notice of the UADE.

1039 • In the case of a device system component malfunction (e.g. pump, CGM, control
1040 algorithm), information will be forwarded to the responsible manufacturer by the study
1041 personnel.

1042 **11.10 Stopping Criteria**

1043 **11.10.1 Participant Discontinuation**

1044 Rules for discontinuing study device use are described below.

1045 • The investigator believes it is unsafe for the participant to continue on the intervention.
1046 This could be due to the development of a new medical condition or worsening of an
1047 existing condition; or participant behavior contrary to the indications for use of the
1048 device that imposes on the participant's safety

1049 • The participant requests that the treatment be stopped

1050 • The participant tests positive for COVID-19 (during study testing or otherwise within 14
1051 days of study start) or subsequently develops symptoms for COVID-19 and tests positive.

1052 • Two distinct episodes of DKA, or one distinct episode of DKA attributable to study device
1053 use.

1054 • Two distinct severe hypoglycemia events meeting the definition in section 11.2.1 of the
1055 protocol, or one distinct severe hypoglycemia event attributable to study device use and
1056 meeting the definition in section 11.2.1 of the protocol.

1057 **11.10.2 Suspending/Stopping Overall Study**

1058 In the case of an unanticipated system malfunction resulting in a severe hypoglycemia or severe
1059 hyperglycemia event (as defined in section 11.2.2), use of the study device system will be
1060 suspended while the problem is diagnosed.

1061 In the event that two distinct episodes of DKA or two distinct severe hypoglycemia events as
1062 defined in section 11.2 occur, the overall study would be suspended while the underlying
1063 conditions are determined.

1064 In addition, study activities could be similarly suspended if the manufacturer of any constituent
1065 study device requires stoppage of device use for safety reasons (e.g. product recall). The affected
1066 study activities may resume if the underlying problem can be corrected by a protocol or system
1067 modification that will not invalidate the results obtained prior to suspension. The Study PI will
1068 review all adverse events and adverse device events that are reported during the study. The

CLINICAL PROTOCOL

1069 Study PI may request suspension of study activities or stoppage of the study is deemed necessary
1070 based on the totality of safety data available.

1071 **11.11 Independent Safety Oversight**

1072 A Data and Safety Monitoring Board (DSMB) will review compiled safety data at periodic intervals. In
1073 addition, the DSMB will review all DKA and severe hypoglycemia irrespective of relatedness to study
1074 device use, and all serious events (including UADEs) related to study device use at the time of
1075 occurrence. The DSMB can request modifications to the study protocol or suspension or outright
1076 stoppage of the study if deemed necessary based on the totality of safety data available. Details
1077 regarding DSMB review will be documented in a separate DSMB document.

1078 **11.12 Definition of a Data Breach**

1079 A data breach is defined in the HITECH Act (43 USC 17932) as an unauthorized acquisition, access,
1080 or use of protected health information (PHI) that compromises the security or privacy of such
1081 information.

1082 **Chapter 12 Miscellaneous Considerations**

1083 **12.1 Prohibited Medications, Treatments, and Procedures**

1084 Participants using glulisine at the time of enrollment will be asked to contact their personal
1085 physician to change their prescribed personal insulin to lispro or aspart for the duration of the
1086 trial.

1087 The study devices (study insulin pump, study CGM) must be removed before Magnetic Resonance
1088 Imaging (MRI), Computed Tomography (CT) or diathermy treatment. Participants may continue
1089 in the trial after temporarily discontinuing use if requiring one of the treatments above.

1090 **12.2 Participant Withdrawal**

1091 Participation in the study is voluntary. Participant may withdraw at any time. For participants
1092 who do withdraw from the study, the study team will determine if their data will be used in
1093 analysis.

1094 **12.3 Confidentiality**

1095 For security and confidentiality purposes, subjects will be assigned an identifier that will be used
1096 instead of their name. Protected health information gathered for this study may be shared with
1097 the third-party collaborators. De-identified subject information may also be provided to
1098 collaborators involved in the study after the appropriate research agreement has been executed.

1099 **Chapter 13 Statistical Consideration**

1100 **13.1 Statistical and Analytical Plans**

1101 We will conduct a paired comparison of outcomes between each admission (FCL vs. FCL+, HCL vs
1102 FCL, and FCL+ vs HCL), using Student paired t-test for percent in ranges and average CGM, and
1103 Wilcoxon test for overtly non normally distributed residuals (which often occur with outcomes
1104 such as % time below 70mg/dL, as well as 50, or 60mg/dL, and % time above 250mg/dL).
1105 Furthermore, we will use repeated measure ANOVA 3x2 with within factors and contrasts (to
1106 differentiate the repeated measures) if covariates are deemed necessary in the analysis.

1107 We do not plan to correct for multiple comparisons.

1108 We do not expect substantial missing values in this highly supervised study, but if more than 3
1109 subjects have one or more missing admissions, we will consider switching from RANOVA to mixed
1110 model repeated measures.

1111 **13.2 Statistical Hypotheses**

1112 The hypotheses for the primary outcome are:

1113 a. Null Hypothesis: There is no difference in the time spent in the 70-180mg/dL range within the
1114 breakfast postprandial period (mealtime to mealtime+5h) between FCL and FCL+ (without and
1115 with anticipation respectively)

1116 b. Alternative Hypothesis: There is a difference in the time spent in the 70-180mg/dL range within
1117 the breakfast postprandial period (mealtime to mealtime+5h) a between FCL and FCL+ (without
1118 and with anticipation respectively).

1119 **13.3 Design and Randomization**

1120 The main study is itself a pilot study to assess glycemic responses to three different approaches
1121 to insulin dosing for carbohydrate ingestion, with different approaches to the RocketAP system
1122 (1) without the meal anticipation module and without carbohydrate announcement (FCL), 2) with
1123 the meal anticipation module on and without carbohydrate announcement (FCL+), or 3) with the
1124 meal anticipation module on and with carbohydrate announcement (HCL), in random order).

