476 **6.4 Admission Check-In**

477 For the pilot study, one to two participants will be assessed at a time. The participant will arrive
478 at the hotel or rental house on the first day of the admission. The study team will perform vital
479 signs, and any changes to the participant's medical history. Any changes to medical history will
480 be communicated to the medical physician to ensure continued eligibility and participation.

481 A urine pregnancy test will be collected if relevant. The test must be negative for the participant
482 to continue with the study.

483 The subject's CGM reading, and ketone concentration will be recorded. In the event that the
484 participant's CGM reading is not between 80-250 mg/dL or ketone concentration is ≥ 0.6 mmol/L
485 prior to initiation of the UVa AP system, the study physician may recommend additional insulin
486 dosing according to the participants' usual doses. Study physician may elect to cancel
487 participant's participation in the hotel admission if concerned about their medical safety. This
488 participant will not be replaced.

489 The participant's home insulin pump will be discontinued, and the study Tandem research insulin
490 pump will be initiated. The study team will ensure the proper function of the CGM, insulin pump,
491 and activity tracker. The goal will be to initiate Closed-Loop Control by approximately lunch time,
492 running the RocketAP system on the DiAs platform.

493 The CGM used in the study is FDA-approved for the non-adjunctive measurement of blood
494 glucose (i.e. the CGM reading can be used for insulin dosing decisions). The CGM readings will be
495 the primary source of blood glucose values. There are no protocol fingerstick blood glucose
496 measurements other than at times of CGM calibration (if necessary) and if directed by the study
497 team. Fingerstick blood glucose measurements may be taken whenever participants experience
498 symptoms, if the CGM glucose is suspected to be erroneous, or any time the participant would
499 like to be reassured.

500 **6.5 Study Meals**

501 Participants will eat a structured dinner at approximately 6-7 pm during the admission. The
502 participant will not announce carbohydrate ingestion, allowing testing of the RocketAP
503 controller. Throughout the Pilot study, the participant will remain in closed loop mode.

504 Participants will consume approximately 30-90 grams of carbohydrates at each meal. The study

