566 mg/dL; this may require contact with the study physician prior to arrival on the day of the
567 study visit
- 568 • Should any concerns regarding medical history, pump information, or unforeseen issues
569 arise, the admission will be cancelled for that participant at the discretion of the
570 investigator

571 **7.5 Admission Check-In**

572 Day 0 Arrival

573 Participants will arrive at the hotel on the first day of the admission. The study team will inquire
574 about any changes to the participant's medical history. Any changes to medical history will be
575 communicated to the medical physician to ensure continued eligibility and participation.

576 A new CGM sensor will be placed if the sensor has not been changed within the last 24-48 hours.

577 Participants will be provided unstructured dinner (no meal-time restrictions). Participants are on
578 their home devices overnight and, therefore, no study staff are required to be present.

579 Day 1 Morning

580 The study team will perform vital signs. The subject's CGM reading, and ketone concentration
581 will be recorded. In the event that the participant's CGM reading is not between 80-250 mg/dL
582 or ketone concentration is ≥ 0.6 mmol/L prior to initiation of the UVa artificial pancreas system,
583 the study physician may recommend additional insulin dosing according to the participants' usual
584 doses. Study physician may elect to cancel participant's participation in the hotel admission if
585 concerned about their medical safety. This participant will not be replaced. A urine pregnancy
586 test will be collected for female participants of childbearing age within 24 hours prior to

CLINICAL PROTOCOL

587 transitioning to the AP Controller. The test must be negative for the participant to continue with
588 the study.

589

590 The participant's home insulin pump will be discontinued, and the study insulin pump will be
591 initiated. The insulin site will be changed and the participants may use the Tandem t:AP2 pump
592 without the DiAs platform for basal delivery until transition to AP. The study team will ensure the
593 proper function of the CGM, insulin pump, and activity tracker.

594 The CGM used in the study is FDA-approved for the non-adjunctive measurement of blood
595 glucose (i.e. the CGM reading can be used for insulin dosing decisions). The CGM readings will be
596 the primary source of blood glucose values. There are no protocol fingerstick blood glucose

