625 admission. Participants may leave the hotel to be outside, provided they are accompanied by a
626 study staff member and masking and distancing are observed, as described in Section 10.3.
627 Participants will enjoy quiet activities in the evening.

628 **7.8 Admission Discharge**

629 Discharge will be at approximately 4 pm. If the CGM values are above 300 mg/dL and ketone
630 values are >0.6 mmol/L, the study team will check the insulin pump infusion site and correction
631 insulin will be administered per study physician judgement via the subject's insulin pump. A
632 qualified clinical study team member (e.g. MD, NP, CDE) will assess and discuss the transition
633 back to usual care with the study participant. Study team will reference the Glycemic Treatment
634 Guidelines.

635 Participants will be asked to continue monitoring ketone levels for 24-48 hours after the hotel
636 admission if ketones were present at time of discharge. Urine ketone supplies may be provided
637 for this testing.

638 **7.9 Post Admission Check-In Visit**

639 Approximately 24-48 hours after the hotel admission, the study team will contact the participant
640 via phone/email/text to assess adverse events, adverse device effects, and device issues.

641

642 **Chapter 8 Glycemic Treatment Guidelines**

643 The following guidelines will be used for both the Pilot Study and the Main Study Admissions to
644 the hotel/rental house.

645 The study physician will suggest appropriate treatment if CGM is <70 mg/dL or >250 mg/dL, or
646 ketone test is >0.6 mmol/L at the start of the hotel admission. The study subject may continue
647 participation in the trial once CGM is between 70-250 mg/dL and ketone concentration is ≤0.6
648 mmol/L.

649 If CGM <60 mg/dL at any time, subjects will be given approximately 8-16 grams of fast-acting
650 rescue carbohydrates. Study team will monitor CGM rise and will consider treating again if CGM
651 <80 mg/dL after approximately 15-20 minutes. Hypoglycemic treatments can occur at any time
652 per study physician request. Glucagon will be available at the study site and will be administered
653 in the event of loss of consciousness or seizure related to hypoglycemia.

654 The study team may request fingersticks as needed. Any fingerstick readings obtained will be
655 addressed the same way as the CGM values.

656 If CGM is >250 for more than 3 hours or >400 mg/dL at any time, study physician will

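### Before the AP system starts, Sections 6.4 and 7.5 name only extra insulin for a CGM reading outside 80-250 mg/dL, the wrong direction for a low reading, and their limits differ from Chapter 8

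*Combined protocol and SAP*

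**What the plan says.** **Section 7.5, Day 1 morning (main study).** CGM and ketone are recorded. The trigger is that the "CGM reading is not between 80-250 mg/dL" or that ketone is 0.6 mmol/L or higher, "prior to initiation of the UVa artificial pancreas system". In that case "the study physician may recommend additional insulin dosing according to the" participant's usual doses. The physician may also cancel the admission on safety grounds.

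**Section 6.4 (pilot).** The rule is the same: "CGM reading is not between 80-250 mg/dL or ketone concentration is" 0.6 mmol/L or higher, with the same two options.

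**Chapter 8 (both admissions).** "The study physician will suggest appropriate treatment if CGM is <70 mg/dL or >250 mg/dL, or" "ketone test is >0.6 mmol/L at the start of the hotel admission". The participant may go on once CGM is 70-250 mg/dL and ketone is 0.6 mmol/L or lower. Separately, a CGM below 60 mg/dL at any time calls for about 8-16 g of fast-acting carbohydrate, and the physician may ask for hypoglycemia treatment at any time.

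**Cross-reference.** Section 7.5 places the Glycemic Treatment Guidelines in a separate document. Sections 5.3.2, 6.5, 7.3 and 7.6 place them in Chapter 8.

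**The concern.** The trigger in 6.4 and 7.5 is two-sided, but the treatment attached to it fits only the high side. A CGM reading below 80 mg/dL meets the trigger, and the one treatment named would lower glucose further. Neither section mentions carbohydrate, a recheck or a delayed start.

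Two sets of limits also appear to govern the decision to start the system. A participant at 75 mg/dL, or with ketone of exactly 0.6 mmol/L, needs attention under one text and may proceed under the other.

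The stake is procedural safety. This is the last listed glucose and ketone check before a device that Section 10.2 classes as significant risk begins automated dosing. The pre-admission contact (6.3, 7.4) sets only an upper goal, below 200 mg/dL on arrival, so no earlier listed step looks for a low reading. The separate-document remark in 7.5 also fails to send its reader to the chapter that would supply the right response.

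**Working it through.** The plan gives no figure to reproduce, so the check sets the texts side by side. CGM is taken in whole mg/dL, with the range ends counted as in range.

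| Reading before AP start | 6.4 and 7.5 | Chapter 8, start of admission |
|---|---|---|
| CGM below 60 | Flagged; insulin is the only treatment named | Treatment required, carbohydrate specified, hold until 70-250 |
| CGM 60-69 | Flagged; insulin is the only treatment named | Treatment required (type not specified), hold until 70-250 |
| CGM 70-79 | Flagged; insulin is the only treatment named | Cleared; only the general physician-request permission applies |
| CGM 80-250 | Not flagged | Cleared |
| CGM above 250 | Flagged; insulin fits | Treatment required, hold |
| Ketone below 0.6 | Not flagged | Cleared |
| Ketone exactly 0.6 | Flagged | Cleared |
| Ketone above 0.6 | Flagged | Treatment required, hold |

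**Direction.** Insulin is the wrong direction in the first three rows, that is, for every CGM reading below 80 mg/dL. In the first two, Chapter 8 supplies a required treatment and a hold. In the third it does not.

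**Limits.** The lower CGM limits differ by 80 - 70 = 10 mg/dL, covering readings of 70-79. The upper limit, 250, agrees. The ketone rules differ at the single value 0.6 (at least 0.6 against above 0.6).

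**Same check or two checks?** In the pilot, 6.4 takes the reading at arrival check-in and before system start, so both rules apply to one reading. In the main study, arrival is on Day 0, participants spend that night on "their home devices overnight and, therefore, no study staff are required to be present", and 7.5 lists no glucose or ketone measurement until Day 1 morning. If Chapter 8's start means Day 1, the rules again meet on one reading. If it means Day 0 arrival, they apply at different times, and 7.5 lists no measurement to which the Chapter 8 rule would apply. The first reading is more natural, but the text does not settle it.

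**Which ketone limit is the outlier?** Chapter 8 uses above 0.6 as its ketone action limit at the start, during the stay and at discharge, apart from a separate escalation step at 3.0 mmol/L. The discharge rules in 6.7 and 7.8 also use above 0.6. Only 6.4 and 7.5 use at least 0.6.

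**The case against.** The strongest reply is that no one is directed to give insulin for a low reading. The sentence says the physician may recommend it, at usual doses, and the next sentence allows cancellation. Read sensibly, it permits insulin where insulin fits. Chapter 8 handles true lows, staff are trained in it (7.3), and CGM is monitored continuously (1.3.5). Readings of 70-79 mg/dL lie inside the primary endpoint range of 70-180, and the protocol counts hypoglycemia events from below 70 (13.5.2). A stricter limit just before AP start than at admission could also be deliberate.

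Most of this stands, and it rules out several stronger readings that a reader might infer:

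- **That the plan orders insulin for hypoglycemia.** It does not; the wording is discretionary, and a physician can comply with both texts.
- **That all readings from 60 to 79 mg/dL lack a suitable response.** Chapter 8 requires treatment and a hold below 70, so the uncovered band is 70-79.
- **That the main study contains a flat contradiction.** Day 0 arrival and the Day 1 check can be read as two time points.
- **That Chapter 8 itself supports 80 as the start limit.** It considers repeat treatment below 80, but only after a reading below 60 has been treated, so this does not conflict with a start limit of 70.

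The reply does not remove the mismatch between trigger and named treatment in 6.4 and 7.5. Nor does it explain the two sets of limits in the pilot, where there is only one check.

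**Conclusion.** The point holds as a drafting error in a safety rule. Sections 6.4 and 7.5 name a treatment that is wrong for the low side of their own trigger, and their limits disagree with Chapter 8 over 10 mg/dL of CGM (70-79) and at one ketone value (0.6 mmol/L). The disagreement is direct in the pilot. In the main study it depends on reading Chapter 8's start of admission as the Day 1 check.

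Practical risk is limited by physician discretion and by the Chapter 8 treatment and hold below 70. The documents give no rate of such readings, so the number of participants affected cannot be stated. A reader might infer harm to the trial's conclusions, but nothing here bears on power, randomization or the primary analysis. It merits correction at the next amendment.

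**What to change.** 1. In 6.4 and 7.5, limit additional insulin to CGM above 250 mg/dL or raised ketones, and not while CGM is below the lower limit.
2. For CGM below the lower limit, state treatment by the study physician under Chapter 8, with carbohydrate as needed, and hold the AP start until CGM is in range. In the main study this is workable, because 7.5 already lets the study pump run "without the DiAs platform for basal delivery until transition to AP".
3. Use one lower CGM limit in 6.4, 7.5 and the Chapter 8 start sentences. Whether it is 70 or 80 mg/dL is for the clinical team to decide on safety grounds.
4. Change the ketone limit in 6.4 and 7.5 to above 0.6 mmol/L. Moving only the Chapter 8 start sentences to the stricter form would split that chapter and leave it at odds with 6.7 and 7.8.
5. In 7.5, point to Chapter 8 in place of a separate document. If Chapter 8's start is meant to be the Day 1 check in the main study, say so there.

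The cost is a wording amendment with IRB approval, which can be bundled with the next one. In operation it means at most an occasional short delay in AP start. In the main study that delay falls on Day 1 morning, ahead of the analysis window that opens at 4 pm (13.5.2).
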